# **Clinical Study Protocol**

## **Johnson & Johnson Vision Care, Inc.**

Refer to the Investigator Brochure for additional information.

## **2. STUDY OBJECTIVES, ENDPOINTS AND HYPOTHESES**

### **2.1. Objectives**

The intent of this study is to demonstrate that the Test lens provides visual benefits under conditions for which it was designed. All mentions of broadband glare, or just glare, are referring to an ecologically-valid light source that emulates sunlight in spectral content.

Phase 1:

1. Primary Objective(s):
  - The primary objective is to help ensure that the glare source intensity will reduce mean contrast sensitivity by about 0.1 log units at 6 cpd (ANSI Z80.12-2007).

Phase 2:

1. Primary Objective(s):
  - The primary objective is to evaluate the visual performance characteristics of a new HEV-filter under conditions where an ecologically-valid light source is present.

### **2.2. Endpoints**

Phase 1:

1. Primary Endpoint(s):
  - Photopic (~120 cd/m^2) contrast sensitivity at 6 cpd with and without a broadband glare source. Testing will include 8 reversals with the last 4 being averaged to provide the contrast threshold.
  - Mesopic (~3 cd/m^2) contrast sensitivity at 6 cpd with and without a broadband glare source. Testing will include 8 reversals with the last 4 being averaged to provide the contrast threshold.

# **Clinical Study Protocol**

## **Johnson & Johnson Vision Care, Inc.**

Phase 2:

1. Primary Endpoint(s):

- Resolution acuity using Landolt C's under bright light conditions (~120 cd/m^2) with a broadband glare source. The photopic resolution acuity on arcminute scale will be converted to logMAR scale for the analysis purpose using  $logMAR = log_{10}(arcminute)$ , see Statistical Analysis Section for more information (Section 14).

2. Secondary Endpoint(s):

- Photopic contrast sensitivity under bright light conditions (~120 cd/m^2) with a broadband glare source. Testing will include 8 reversals with the last 4 being averaged to provide the contrast threshold.
- Mesopic contrast sensitivity under dim light conditions ( $\leq 3$  cd/m^2) with a broadband glare source. Testing will include 8 reversals with the last 4 being averaged to provide the contrast threshold.

### **2.3. Hypotheses**

Phase 1:

The least-square means (LSM, i.e., adjusted means) of photopic contrast sensitivity and mesopic contrast sensitivity at 6 cpd will be estimated with 95% confidence interval separately under conditions with glare source and without glare source. The primary endpoints in phase 1 will not be statistically tested, and consequentially statistical inferences will not be made. Instead, the reduction in the estimated mean for photopic and mesopic contrast sensitivity due to the glare source will be compared against the criteria of 0.1 log (per ANSI Z80.12-2007). If the reduction in the estimated mean due to the glare source is about 0.1 log units, then it can be concluded that the glare light source is effective and the study can move to Phase 2.

Phase 2:

1. Primary Hypothesis:

- The Test lens will provide improved photopic resolution acuity than the Control lens under conditions of a broadband glare source.

2. Secondary Hypotheses

- The Test lens will provide improved photopic contrast sensitivity than the Control lens under conditions of a broadband glare source.
- The Test lens will provide improved mesopic contrast sensitivity under conditions of a broadband glare source.

Phase 2: The primary hypothesis must be met to satisfy the objective of the study. The secondary hypotheses will be evaluated only when the primary hypothesis is met. For both primary and secondary endpoints, in addition to the statistical testing, the model-based point estimate of mean difference will be evaluated against a predetermined clinically meaningful margin (0.05 logMAR for visual acuity and 0.06 log for both photopic and mesopic contrast sensitivity).

# **Clinical Study Protocol**

## **Johnson & Johnson Vision Care, Inc.**

### **3. TARGETED STUDY POPULATION**

#### **3.1. General Characteristics**

Subjects must be habitual wearers of silicone hydrogel contact lenses worn on a daily wear basis. Subjects can be of any gender, race, and ethnicity that meet the eligibility criteria. Subjects enrolling in phase 1 or phase 2 will largely have the same eligibility criteria except where noted.

Subject who participate in phase 1 of the study will not participate in phase 2 of the study.

#### **3.2. Inclusion Criteria**

##### **3.2.1. Phase 1 Inclusion Criteria**

Potential subjects must satisfy all of the following criteria to be enrolled in the study:

Inclusion Criteria following Screening

The subject must:

1. Read, understand, and sign the STATEMENT OF INFORMED CONSENT and receive a fully executed copy of the form.
2. Appear able and willing to adhere to the instructions set forth in this clinical protocol.
3. Be between 18-39 (inclusive) years of age at the time of screening.
4. By self-report, habitually wear spherical silicone hydrogel soft contact lenses in both eyes in a daily reusable or daily disposable wear modality (i.e. not extended wear modality). Habitual wear is defined as a minimum of 6 hours of wear per day, for a minimum of 5 days per week during the past 30 days.
5. Possess a wearable pair of spectacles that provide correction for distance vision.
6. Habitual spherical contact lens powers must be between -1.00 D and -6.00 D (inclusive) in each eye.

Inclusion Criteria following Baseline Evaluation

7. Habitual contact lenses must provide at least 20/20 acuity OD and OS

##### **3.2.2. Phase 2 Inclusion Criteria**

Potential subjects must satisfy all of the following criteria to be enrolled in the study:

Inclusion Criteria following Screening

The subject must:

1. Read, understand, and sign the STATEMENT OF INFORMED CONSENT and receive a fully executed copy of the form.
2. Appear able and willing to adhere to the instructions set forth in this clinical protocol.
3. Be between 18 and 70 (inclusive) years of age at the time of screening.
4. By self-report, habitually wear spherical silicone hydrogel soft contact lenses in both eyes in a daily reusable or daily disposable wear modality (i.e. not extended wear

# **Clinical Study Protocol**

## **Johnson & Johnson Vision Care, Inc.**

modality). Habitual wear is defined as a minimum of 6 hours of wear per day, for a minimum of 5 days per week during the past 30 days.

5. Possess a wearable pair of spectacles that provide correction for distance vision.

### Inclusion Criteria following Baseline Evaluation

6. The spherical equivalent of the subject's vertex-corrected distance refraction must be between -1.00 D and -6.00 D (inclusive) in each eye.
7. The magnitude of the cylindrical component of the subject's vertex-corrected distance refraction must be between 0.00 D and 1.00 D (inclusive) in each eye.
8. The best corrected, monocular, distance visual acuity must be 20/25 or better in each eye.

### **3.3. Exclusion Criteria**

#### **3.3.1. Phase 1 Exclusion Criteria**

Potential subjects who meet any of the following criteria will be excluded from participating in the study:

### Exclusion Criteria following Screening

The subject must not:

1. Be currently pregnant or lactating.
2. Be currently using any ocular medications or have any ocular infection of any type.
3. By self-report, have any ocular or systemic disease, allergies, infection, or use of medication that might contraindicate or interfere with contact lens wear, or otherwise compromise study endpoints, including infectious disease (e.g., hepatitis, tuberculosis), contagious immunosuppressive disease (e.g., Human Immunodeficiency Virus [HIV]), autoimmune disease (e.g. rheumatoid arthritis, Sjögren's syndrome), or history of serious mental illness or seizures. See section 9.1 for additional details regarding excluded systemic medications.
4. Have habitually worn rigid gas permeable (RGP) lenses, orthokeratology lenses, or hybrid lenses (e.g. SynergEyes, SoftPerm) within the past 6 months.
5. Be currently wearing monovision or multifocal contact lenses.
6. Be currently wearing lenses in an extended wear modality.
7. Have participated in a contact lens or lens care product clinical trial within 30 days prior to study enrollment.
8. Be an employee (e.g., Investigator, Coordinator, Technician) or immediate family member of an employee (including partner, child, parent, grandparent, grandchild or sibling of the employee or their spouse) of the clinical site.

### Exclusion Criteria following Baseline Evaluation

The subject must not:

9. Have clinically significant (grade 3 or higher on the FDA grading scale) slit lamp findings (e.g., corneal edema, neovascularization or staining, tarsal abnormalities or bulbar injection) or other corneal or ocular disease or abnormalities that contraindicate contact lens wear or may otherwise compromise study endpoints (including entropion,

# **Clinical Study Protocol**

## **Johnson & Johnson Vision Care, Inc.**

ectropion, chalazia, recurrent styes, glaucoma, history of recurrent corneal erosions, aphakia, moderate or above corneal distortion, herpetic keratitis).

10. Have a history of strabismus or amblyopia.
11. Have fluctuations in vision due to clinically significant dry eye or other ocular conditions.
12. Have had any ocular or intraocular surgery (e.g., radial keratotomy, PRK, LASIK, iridotomy, retinal laser photocoagulation, etc.).
13. Have signs of a contact lens-related corneal inflammatory event (e.g., past peripheral ulcer or round peripheral scar).
14. Have a history of eyelid injury, surgery or procedure that resulted in abnormal eyelid position or movement.

### **3.3.2. Phase 2 Exclusion Criteria**

Potential subjects who meet any of the following criteria will be excluded from participating in the study:

#### **Exclusion Criteria following Screening**

The subject must not:

1. Be currently pregnant or lactating.
2. Be currently using any ocular medications or have any ocular infection of any type.
3. By self-report, have any ocular or systemic disease, allergies, infection, or use of medication that might contraindicate or interfere with contact lens wear, or otherwise compromise study endpoints, including infectious disease (e.g., hepatitis, tuberculosis), contagious immunosuppressive disease (e.g., Human Immunodeficiency Virus [HIV]), autoimmune disease (e.g. rheumatoid arthritis, Sjögren's syndrome), or history of serious mental illness or seizures. See section 9.1 for additional details regarding excluded systemic medications.
4. Have habitually worn rigid gas permeable (RGP) lenses, orthokeratology lenses, or hybrid lenses (e.g. SynergEyes, SoftPerm) within the past 6 months.
5. Be currently wearing monovision or multifocal contact lenses.
6. Be currently wearing lenses in an extended wear modality.
7. Have participated in a contact lens or lens care product clinical trial within 30 days prior to study enrollment.
8. Be an employee (e.g., Investigator, Coordinator, Technician) or immediate family member of an employee (including partner, child, parent, grandparent, grandchild or sibling of the employee or their spouse) of the clinical site.

#### **Exclusion Criteria following Baseline Evaluation**

The subject must not:

9. Have clinically significant (grade 3 or higher on the FDA grading scale) slit lamp findings (e.g., corneal edema, neovascularization or staining, tarsal abnormalities or bulbar injection) or other corneal or ocular disease or abnormalities that contraindicate contact lens wear or may otherwise compromise study endpoints (including entropion, ectropion, chalazia, recurrent styes, glaucoma, history of recurrent corneal erosions, aphakia, moderate or above corneal distortion, herpetic keratitis).

# **Clinical Study Protocol**

## **Johnson & Johnson Vision Care, Inc.**

10. Have a history of strabismus or amblyopia.
11. Have fluctuations in vision due to clinically significant dry eye or other ocular conditions.
12. Have had any ocular or intraocular surgery (e.g., radial keratotomy, PRK, LASIK, iridotomy, retinal laser photocoagulation, etc.).
13. Have signs of a contact lens-related corneal inflammatory event (e.g., past peripheral ulcer or round peripheral scar).
14. Have a history of eyelid injury, surgery or procedure that resulted in abnormal eyelid position or movement.

### **3.4. Enrollment Strategy**

Study subjects will be recruited from the Institution/clinical site's subject database and/or utilizing Independent Ethics Committee (IEC) or Institutional Review Board (IRB) approved materials.

## **4. STUDY DESIGN AND RATIONALE**

### **4.1. Description of Study Design**

Phase 1: This is a non-randomized, non-masked, non-dispensing study where subjects will wear their own contact lenses for approximately 1 hour.

Phase 2: This is a controlled, randomized, double-masked, contralateral (Test/Control or Control/Test), non-dispensing study where the study lenses will be worn in a daily wear modality for approximately 3 hours. Subjects will not have access to the study lenses at the conclusion of their visit.

[figure not shown]
### **4.2. Study Design Rationale**

Phase 1: This study phase is to help ensure that the intensity of the glare source is efficacious and satisfies ANSI Z80.12-2007. Subjects will wear their own contact lenses and be tested unilaterally.

Phase 2: This study phase will be executed using a contralateral design. There are several benefits to this choice of design. First, a contralateral design will allow us to compare performance within the same individual, ostensibly with the same baseline light sensitivity by eye. Second, other subject factors that can influence visual performance, such as iris color and absorption of test lights via macular pigment, are better controlled using this design. Third, in psychophysical testing, which is the gold standard for many of the visual functions being tested, participants make judgments about some event threshold, such as when an image disappears. Participants may have different criteria for threshold events that are internally consistent *within* subjects but can vary *between* subjects. A contralateral design allows the investigational lens to be compared within subjects, with consistent criteria for threshold events. Sufficient time will be taken between measures to reduce any potential bias, as follows:

# **Clinical Study Protocol**

## **Johnson & Johnson Vision Care, Inc.**

### **4.3. Enrollment Target and Study Duration**

Phase 1: This phase of the study will enroll up to 24 subjects with the intent of completing 20. This will be conducted at 1 clinical site. A subject will be considered enrolled upon signing of the informed consent form. All subjects will be in the age range 18-39 in accordance with ANSI Z80.12-2007. There will be 1 visit in total per subject lasting approximately one hour. Enrollment period is approximately one week.

Phase 2: This phase of the study will have an enrollment target of 66 subjects, with a goal of at least 60 to complete. The subjects in phase 2 will not include the subjects from phase 1. The study will be conducted at 1 clinical site (same site as phase 1). A subject will be considered enrolled upon signing of the informed consent form. Approximately 30 subjects (+/- 5) will be in the age range 18-39, with the remainder comprising the 40-70 year old group. There will be 1 visit in total per subject. Total duration of phase 2 is expected to be approximately 8 weeks.

Total study duration (phase 1 + interim analysis + phase 2) is expected to last about 10 weeks. Subjects who are discontinued prior to the final evaluation may be replaced at the discretion of the study sponsor. The investigation will end at the time that the study data is hard locked.

# **Clinical Study Protocol**

## **Johnson & Johnson Vision Care, Inc.**

### **5. TEST ARTICLE ALLOCATION AND MASKING**

#### **5.1. Test Article Allocation**

Phase 1: Not Applicable. Subjects are wearing their habitual contact lenses.

Phase 2: Use of the test articles will be randomized using a lens fitting schedule supplied by the study biostatistician. The clinical site will follow the lens fitting schedule provided and will complete enrollment according to the randomization list and will not pre-select or pre-assign subjects.

Randomly-permuted block randomization will be used to avoid bias in the assignment of subjects to treatment and to enhance the validity of statistical comparisons across treatment groups. Subjects, in blocks of two, will be randomized to either wear the Test lens in the left eye and the Control lens in the right eye or the Control lens in the left eye and the Test lens in the right eye. The order of the light sources is predetermined: visual performance will be assessed under the no broadband light source (without glare) condition first and then assessed under the broadband light source (with glare) condition. The same randomization scheme will be used for these two light sources. Under each light source condition, the right eye will always be tested first. Subjects will be stratified into one of two age groups (18-39 years old and 40-70 years old) using a 1:1 allocation ratio. The randomization scheme will be generated using the PROC PLAN procedure from Statistical Analysis System (SAS) Software Version 9.4 or higher (SAS Institute, Cary, NC).

Randomization will be performed at phase 2 visit 1. The following must have occurred prior to randomization:

- Informed consent must have been obtained.
- The subject must have met all eligibility criteria.
- The subject's screening and baseline information must have been collected.

When releasing test articles for vision testing, the following steps should be followed to maintain randomization codes:

1. Investigator or designee (documented on the Delegation Log) will consult the lens fitting schedule to obtain the test article assignment for that subject prior to dispensing.
2. Investigator or designee will record the subject's number on the appropriate line of the lens fitting schedule.
3. Investigator or designee will pull the appropriate test articles from the study supply. All test articles that are opened, whether dispensed (placed/fit on eye or dispensed outside the clinical site) or not, must be recorded on the Test Article Accountability Log in the "Dispensed" section.

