### **5.3. Procedures for Maintaining and Breaking the Masking**

Every attempt will be made to keep the clinical trial personnel involved in the study (e.g. data management, biostatistician and clinical operations) unaware of the identity of the assigned study lenses. The identity of the study lenses will be masked by having the blister packs labeled with the study number, lot number, sphere power, expiration date and the randomization codes. Only the unmasked biostatistician generating the lens fitting schedule will have access to the decode information that allows matching of the randomization codes to the test articles. The medical monitor will also have access to the decode information in case breaking the mask is necessary for the urgent medical treatment of a subject.

Under normal circumstances, the mask should not be broken until all subjects have completed the study and the database is finalized. Otherwise, the mask should be broken only if specific emergency treatment/course of action would be dictated by knowing the treatment status of the subject. In such cases, the investigator may, in an emergency, contact the medical monitor. In the event the mask is broken, the sponsor must be informed as soon as possible. The date, time, and reason for the unmasking must be documented in the subject record. The investigator is also advised not to reveal the study treatment assignment to the clinical site or sponsor personnel.

Subjects who are discontinued will be replaced.

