**Clinical Study Protocol**  
**Johnson & Johnson Vision Care, Inc.**

Phase 2: Visit 1: Treatment 1 Lens Fitting		
Step	Procedure	Details
1.23	Lens Selection	
Assign the study lens based on the randomization scheme provided by the biostatistician.
 
Select the contact lens power [REDACTED] based on vertexed spherical equivalent from the refraction.

1.24	Lens Insertion	
The Investigator or the subject inserts the study lenses. Record the time of lens insertion.
 
Check for lens damage under the slit lamp before proceeding with lens settling.
 
Replace damaged lenses if applicable.
 
Ensure the subject is given a Patient Instruction Guide.

1.25	Lens Settling	Allow the study lenses to settle for a minimum of 5 minutes.
1.26	Subjective Best Sphere Over Refraction	Perform subjective best sphere refraction over the study lenses (adopt the maximum plus to maximum visual acuity (MPMVA) approach).
1.27	Lens Power Modification (if applicable)	
Adjust the lens power if the subject's best sphere over-refraction is not plano.
 
For each power modification, select the adjusted fitting lens power as appropriate and repeat steps 1.12 through 1.14.
 
Up to two power modifications are allowed per eye.

1.28	Subject Reported Ocular Symptoms	Subjects will respond to a verbal open-ended symptoms questionnaire.
1.29	Visual Acuity	Record the best corrected Snellen distance visual acuity to the nearest letter (OD and OS). Subjects must read the smallest line until at least 50% of the letters are read incorrectly. Visual acuity with the study contact lenses must be 20/30 or better OD and OS.

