**Clinical Study Protocol**  
**Johnson & Johnson Vision Care, Inc.**

Phase 2: Visit 1: Treatment 1 Lens Fitting		
Step	Procedure	Details
1.30	General Lens Fit Assessment	
Evaluate lens centration, movement on blink, and push-up test for each eye.
 
An unacceptable fit is deemed by one of the following criteria:
 
 
• limbal exposure at primary gaze or with extreme eye movement.
 
• edge lift.
 
• excessive movement in primary and up gaze.
 
• insufficient movement in all three of the following conditions: primary gaze, up gaze, and push-up test.
 
 
Note: if lens fit is unacceptable for either eye, the subject will be discontinued from the study.

1.31	Continuance	
For the subject to continue in the study, they must meet all three of the following criteria:
 
 
1. Visual acuity is 20/30 or better OD and OS.
 
2. The lens fit is acceptable OD and OS.
 
3. Investigator approval.
 
 
If the Investigator does not approve the study lens, then the study is terminated for that subject.

1.32	Lenses Worn in Clinic	
The lenses will be released for approximately two hours.
 
 
1. The subjects must wear both study lenses the entire time.
 
2. The lenses will be worn as daily wear only.
 
3. Rewetting drops are permitted if needed.
 
 
Note: In the event a lens is lost or damaged, it will be replaced immediately.
 
Note: A clinic-only-wear Patient Instruction Guide will be provided.

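### Fixed, disclosed blocks of two make about half of the Phase 2 left/right assignments deducible, and no concealment of the lens fitting schedule is described

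*Combined protocol and SAP*

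**What the plan says.** Section 5.1: "Use of the test articles will be randomized using a lens fitting schedule supplied by the study biostatistician". The method is permuted blocks: "Randomly-permuted block randomization will be used to avoid bias in the assignment of subjects to treatment". The block size is fixed and stated: "Subjects, in blocks of two, will be randomized to either wear the Test lens in the left eye" with Control in the right eye, or the reverse. "Subjects will be stratified into one of two age groups (18-39 years old and 40-70 years old) using a 1:1 allocation ratio". The investigator or designee consults the schedule for the assignment, and then "Investigator or designee will record the subject's number on the appropriate line of the lens fitting schedule". The site is told to follow the list and not to select subjects in advance. Consent, eligibility and baseline data must precede randomization.

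Section 4.3 gives one clinical site, a target of 66 enrolled and at least 60 completing, and defines enrolment as signing consent.

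Section 5.3 says blister packs are "labeled with the study number, lot number, sphere power, expiration date and the randomization codes". Access to the decode is limited to the unmasked biostatistician and, for emergencies, the medical monitor.

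In section 7.2 (Phase 2), each eye's refraction and acuity are recorded at step 1.19, dominance at 1.20, eligibility at 1.22 and assignment at 1.23. At step 1.24 "The Investigator or the subject inserts the study lenses", and the lenses are checked for damage at the slit lamp. At step 1.31 continuation needs investigator approval: "If the Investigator does not approve the study lens, then the study is terminated for that subject".

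**The concern.** In a contralateral trial every subject wears both lenses, so randomization protects one thing only: which eye receives Test. With a known block size of two, anyone who knows the first subject's pattern in a block knows the second's. If unused lines of the schedule can also be read, every coded pattern is known. The plan describes no sealed, staged or central release that would prevent this, and an instruction not to pre-select is not a concealment mechanism.

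The remaining barrier is lens identity. Section 1 contrasts an HEV-absorbing lens with an ordinary transparent one, and nothing says the two look alike on handling. Site staff may insert both and do inspect them at the slit lamp. Recognizing one lens in the first subject of a block gives the second subject's assignment without any code being broken. Lot or expiry date could do the same if they differ by product, which the documents do not say.

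A site holding that knowledge could, knowingly or not, judge borderline eligibility in favour of subjects whose better eye is due the Test lens. The primary model in section 14.5 has lens, dominant eye, their interaction and age, but no term for each eye's acuity before the study lenses, so it would not remove such a shift.

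**Working it through.** **1. The plan's own figure.** Table 9, first scenario: difference −0.05 logMAR, SDs 0.08 and 0.09, correlation 0.3, n = 60, two-sided alpha 0.05.
- SD of the paired difference = √(0.08² + 0.09² − 2 × 0.3 × 0.08 × 0.09) = 0.1009.
- SE = 0.1009/√60 = 0.0130.
- Exact paired t power = 0.9653, against 96.5% stated. It reproduces, and the allocation method does not change it.

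**2. Share of patterns fixed by earlier ones.** In a block of two, the second position is determined. I assume an equal split of 66, so 33 per stratum: 16 complete blocks plus one extra subject, giving 16/33 = 48.5%. With complete blocks it is 50%. The best guess is right with probability (0.5 + 1)/2 = 75%.

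| Scheme | Fully determined | Best guess correct |
|---|---|---|
| Fixed 2 (complete blocks) | 50% | 75% |
| Fixed 4 (complete blocks) | 33% | 71% |
| Random 2/4, sizes undisclosed | about 10% | about 72% |
| Random 4/6, sizes undisclosed | about 6% | about 69% |

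The random rows are simulated. Varying the size removes most of the certainty but lowers the best-guess rate only slightly. If unused lines can be read, 100% of coded patterns are known whatever the block size, which is why single release is needed as well.

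**3. What this could do to the primary test (illustration only).** Assume masking has failed, a share f of subjects enter with Test in the truly better eye, and the true interocular difference is normal with SD s. Neither f nor s is in the documents.
- Shift in Test − Control = f × s × √(2/π) = 0.798 × f × s.
- False superiority rate = probability that the upper 95% limit falls below 0, given that shift and SE 0.0130. With no shift it is 2.5%.

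| f | s = 0.03 | s = 0.07 |
|---|---|---|
| 0.10 | shift 0.0024, rate 3.8% | shift 0.0056, rate 6.2% |
| 0.20 | shift 0.0048, rate 5.5% | shift 0.0112, rate 13.2% |

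With masking intact, f has no route to operate and the shift is 0.

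**4. Cost in balance.** A truncated block of 4 leaves at most 2 more of one pattern, so at most 2 per stratum and 4 of 66 overall. If the right eye differs from the left by δ on average (for instance because it is always tested first), the estimate moves by δ × imbalance/n, at most δ × 4/66 = 0.06δ, random in sign. Fixed blocks of two leave at most 1 per stratum, or 2/66 = 0.03δ.

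**The case against.** Several defences stand.
- The format of the schedule is not shown, so whether later lines are visible is unknown. A reader might infer that the site knows the next assignment before it enrols anyone and that allocation is unconcealed. The documents do not support that. Enrolment is consent, eye measurements come after consent, and the assignment is read only after eligibility and baseline are complete. The supportable statement is that concealment is not described and half the patterns are deducible.
- The site sees codes. The decode is restricted (5.3), packs are over-labelled to mask subjects and investigators (6.3), and endpoint investigators are masked (5.2). No section says the lenses look different, that lots differ, or how many codes each lens has.
- Harm is limited by design. Differences between subjects cancel. Each eye must reach 20/25 or better, amblyopia and strabismus are excluded, and the numeric eligibility criteria leave little room for judgement. Dominance, one possible lever, is in the model.
- The illustration gives the site error-free knowledge of the better eye. In practice it has one Snellen acuity under spherocylindrical refraction, so the rates in step 3 lean high.

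These points limit the size of the problem. They do not remove the deducible second position, and appearance at insertion is a route to lens identity that coding does not close.

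**Conclusion.** The point holds as an avoidable weakness in allocation. The block size is fixed, as small as it can be, and printed in the protocol the single site uses, and no mechanism hides unused lines. About half of the left/right patterns (16 of 33 per stratum on an equal split) follow from the preceding one before step 1.22 is decided.

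This becomes knowledge of which eye gets Test only if lens identity is inferred. A reader might take the rates of 3.8% to 13.2% as the trial's expected error rate. They are not: they require failed masking, steering of 10% to 20% of subjects and an interocular SD of 0.03 to 0.07 logMAR, none of which is in the documents. With full masking the bias is zero. The case for change rests on how little it costs, not on evidence of harm.

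**What to change.** - In section 5.1, replace the fixed block size with randomly permuted blocks of randomly varying small size (for example 2 and 4) within each age stratum. The unmasked biostatistician holds the sizes, and they are left out of what the site receives.
- Release each assignment singly and in sequence, by numbered sealed sheets per stratum or through the existing EDC system, only after step 1.22 eligibility is recorded.
- List every subject ended at step 1.31 by assigned eye pattern and reason. That decision follows assignment, so neither change above reaches it. Such subjects have no glare acuity value and, because section 14.9 does not impute, drop out of the primary comparison.

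Cost: revised wording in 5.1, a re-run of the randomization program, a staged release and one listing. No added subjects or visits, and power is unchanged. The downside is a right/left imbalance of at most 2 per stratum, which matters slightly because the right eye is always tested first and the model has no eye term.
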